4. SUBJECT SELECTION

4.0 Subject Recruitment

Participants will be recruited from the UM and UW MS Clinics tertiary clinics. Additional participants will be recruited through UM and UW medical records; other neurology practices throughout Mid- and Southeastern Michigan (by invitation) and the Pacific Northwest, UM and UW electronic clinical trials registries; advertisement through community outlets (e.g., posting flyers in community centers, distributing flyers and fund raising walks), clinicaltrials.gov; Facebook and other social media campaigns, iConquerMS, and from advertisements posted by the NMSS (study stakeholder).

The table below shows the current enrollment plan for data collection.

Total number of study participants expected to be screened:	360
Of those screened, total number of study participants expected to be eligible:	340
Of those eligible, total number of study participants enrolled:	330
Target sample size (i.e., of those eligible, total number of study participants expected to be enrolled):	300 completers

We anticipate enrolling 50 subjects per site in year 1, 65 subjects per site in year 2, and 50 per site subjects in year 3, or an average of 4-5 subjects per month per site throughout the course of the study.

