5.2 Blinding

The subject, PI, co-investigators, interventionists, and coordinators will not be blinded.

5.3 Interventions:

Telephone-based CBT: Cognitive Behavioral Therapy for fatigue (CBT – see table 1), also commonly referred to as “fatigue self-management”, was chosen as a comparator given its endorsement in MS fatigue treatment guidelines based on previous efficacy studies demonstrating its benefits in MS. For this study, we will use telephone-delivered CBT for fatigue self-management, which also has a strong evidence-base for its use in MS patients. Developed and tested by one of our study investigators ([name]), this treatment is routinely utilized in her clinical practice to manage several chronic symptoms in MS including pain, depression, and fatigue in MS. In her primary trial of this intervention using the telephone-delivered treatment, which targeted MS-related pain and depression as well as fatigue, 50% of fatigued participants with MS had a clinically meaningful reduction in pain impact that was maintained at 6- and 12-months post treatment. This treatment will be delivered one-on-one via telephone by study interventionists with special training in CBT for symptom management and in telehealth delivery. The team of psychologists includes Drs. [name], [name], [name], and [name], who are all licensed clinical psychologists, who will supervise the two study interventionists (one per study site). Study interventionists will be either licensed clinical psychologists, clinical psychology pre-doctoral students or postdoctoral fellows, or Master’s level social workers. Currently, the primary interventionists are [name], MSW at UM (Drs. [name] and [name] secondary/back-up interventionists) and [name], MSW, [name], and [name], MS at UW (Drs. [name] and [name] secondary/back-up interventionists).

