6.3 Randomization

Following collection of baseline assessments, participants will be randomized during the baseline screening visit and assigned treatment.

Randomization Process/Blinding: Subjects who meet criteria I/E criteria will be randomized using computer-based randomization via <http://cscar-randomization.appspot.com/> (1:1:1 randomization) to determine whether they will receive telephone based CBT monotherapy (Group 1, n~100), Modafinil monotherapy (Group 2, n~100), or combination therapy with both treatments (Group 3). Statisticians and study staff who process data (subjects will enter data directly into the database, so no study personnel are directly collecting data) will remain blinded to group allocation for the duration of the study. The subject, PI, co-investigators, study interventionists, and coordinators will not be blinded.

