9.0 DATA ANALYSIS/STATISTICAL METHODS

9.1 Sample Size Determination

Estimates are derived from recent data from the study team, and published interventional studies of modafinil and CBT monotherapy. The primary sample size determinant for this study is Aim 1.

For Aim 1, we have chosen the Modified Fatigue Impact Score (MFIS) as the primary outcome variable of interest. The MFIS has been validated in MS patients, is frequently used in MS clinical studies as a reliable measure of fatigue, and is sensitive to changes in intervention. The primary outcome measure will be the mean within-subject difference between baseline and 12-week MFIS values (delta-MFIS), compared between groups. Based on a power analysis of 2-sample means (combined monotherapy groups vs. combination therapy, group weights 2:1), with a 2-sided alpha of 0.05 and standard deviation of 12, a sample size of n=300 subjects will provide 92% power to detect a delta-MFIS of 5 between the monotherapy and combination treatment arms (see power curve); this difference is similar to group differences found in previous fatigue trials.

For Aim 2 analyses, using fatigue outcomes as the dependent variables (in separate models) a multiple linear regression power analysis was performed assuming a full model consisting of up to 11 possible predictor variables: treatment group, presence of sleep disturbance (yes/no), depression severity (PHQ-9 Score), disability severity (EDSS score), 3 interaction terms (treatment*sleep, treatment*depression, and treatment*disability), baseline fatigue level, anxiety, pain, and exercise. A similar model will also be constructed using MS subtype and treatment*MS subtype interaction term, (in place of EDSS) to determine if subtype conveys differences in fatigue outcome separate from pure disability measures. Based on a sample size of n=300, we will have 85% power to detect an R-square difference of 0.04 for the interaction term of interest, assuming the R-squared explained by the adjustment variables is at least 0.3.

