For Aim 3, using treatment adherence as the dependent variable (continuous outcome), a multiple linear regression power analysis was performed assuming a full model consisting of up to 8 possible predictor variables: treatment group (independent variable of interest), age, gender, EDSS score, baseline fatigue level, baseline activity level, presence of sleep disturbance (yes/no), and depression severity (PHQ-9 Score). Based on a sample size of n=300, we will have 95% power to detect an R-square difference of 0.03 for the test predictor of interest, assuming the R-squared explained by the adjustment variables is at least 0.3.

9.2 Analysis of Study Aims:

Aim 1: Compare the effectiveness of 3 therapies: CBT monotherapy, modafinil monotherapy, and CBT+modafinil combination therapy on patient-reported fatigue impact (primary outcome), fatigue intensity, and fatigability among fatigued individuals with MS. The primary outcome measure will be the mean difference in Modified Fatigue Impact Scale (MFIS) score between 12 weeks and baseline (delta-MFIS), compared between treatment groups. A repeated measures mixed effects model will be applied. The mean difference will also be adjusted for baseline covariates: age, gender, anxiety, pain, and exercise, which were included as covariates based on their established association between fatigue and/or activity in MS. Additional secondary analyses will also evaluate treatment effect on EMA outcome measures of fatigue impact, fatigue intensity, and fatigability.

Aim 2: Test whether depression, sleep disturbances, or MS disability level modify comparative treatment responsiveness across treatment arms in terms of fatigue impact (HTE analyses). Treatment group effect on fatigue impact scores, fatigue intensity, and fatigability among select subgroups, including those with clinically significant depression, progressive MS subtype and higher EDSS scores, and confirmed/suspected sleep disorders not related to poor sleep hygiene, will be evaluated with interaction terms in mixed effects models as above.

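### Site is in neither the described randomisation nor the Aim 1 covariate list; a site term would cost almost nothing, although the expected gain is small

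*Combined protocol and SAP*

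**What the plan says.** **Randomisation.** Section 6.3 states that subjects "will be randomized using computer-based randomization via" a named web tool in a 1:1:1 ratio. Section 5.1 gives the same ratio. Neither mentions stratification, blocking or site.

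**Primary model.** Section 9.2 applies a mixed model for repeated measures to delta-MFIS, with the mean difference "adjusted for baseline covariates: age, gender, anxiety, pain, and exercise, which were included as covariates". Site is not listed, and the random effects are not specified. Site is also absent from the Aim 2 predictors and the Aim 3 adherence covariates (Sections 9.1 and 9.2).

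**Sites.** Section 4.0 plans equal enrolment at the Michigan and Washington centres: "We anticipate enrolling 50 subjects per site in year 1, 65 subjects per site in year 2", then 50 per site in year 3. Local recruitment draws on Michigan for one site and the Pacific Northwest for the other.

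**CBT delivery.** Section 5.3 describes licensed psychologists "who will supervise the two study interventionists (one per study site". It then lists separate primary and back-up staff for each centre: one primary interventionist at Michigan and three at Washington. Supervising psychologists also differ by site, under a common manual and fidelity protocol.

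**Power.** Section 9.1 compares "combined monotherapy groups vs. combination therapy, group weights 2:1", "with a 2-sided alpha of 0.05 and standard deviation of 12", and concludes that "a sample size of n=300 subjects will provide 92% power to detect a delta-MFIS of 5".

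**The concern.** Site is known for every participant before treatment starts. It may be related to outcome through patient mix, local practice and who delivers CBT. If it enters neither the allocation nor the model, two things follow. Any average site difference in delta-MFIS stays in the residual variance. And if the arms happen to contain different shares of the two sites, the estimate carries part of the site difference. What is at stake is a little precision and a little chance error in the primary contrast. There is also a practical risk: with no rule fixed in advance, whether to adjust for site could be decided after the data are seen.

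**Working it through.** **1. Inputs.** From Section 9.1: SD 12, difference 5, two-sided alpha 0.05, 300 subjects split 2:1 (100 combination, 200 pooled monotherapy). From Section 4.0: 50 + 65 + 50 = 165 enrolled per site, 330 in all, with a target of "300 completers". Assumed: completers split evenly, 300 / 2 = 150 per site.

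**2. The plan's own power figure.**
- SE = 12 × sqrt(1/100 + 1/200) = 1.47.
- 5 / 1.47 = 3.40.
- Power is 0.925 by normal approximation and 0.924 by noncentral t with 298 df. The stated 92% reproduces.

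**3. Cost of a site term.**
- One df fewer (297) gives 0.924, unchanged to four decimals. With the five listed covariates also in the model (293 vs 292 df) it is 0.924 both ways.
- Worst case: site explains nothing and the arms are unbalanced by chance. Variance inflation averages 1.003 (power 0.923) and is 1.013 at its 95th percentile (power 0.921).

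**4. Possible gain.** If site explains 1%, 2% or 5% of outcome variance (assumed), power becomes 0.926, 0.929 or 0.936. With equal sites, the corresponding site difference is 2 × 12 × sqrt(R-squared) = 2.4, 3.4 or 5.4 points.

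**5. Chance imbalance if allocation is not stratified.** Let x be the number in the combination group who come from one site.
- Hypergeometric variance of x = 100 × 0.25 × 200/299 = 16.7, so its SD is 4.09.
- Difference in site share = x/100 − (150 − x)/200 = 0.015x − 0.75. Its SD is 0.015 × 4.09 = 0.061, or 6.1 percentage points.
- By simulation (200,000 draws), the 95th percentile of the absolute difference is 12 points, and it exceeds 10 points in about 11% of trials.

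**6. Effect on the estimate.** At 12 points of imbalance:
- site difference 2 (assumed): 0.12 × 2 = 0.24 points;
- site difference 4 (assumed): 0.12 × 4 = 0.48 points.

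These are 5% and 10% of the 5-point target, or 0.24/1.47 = 0.16 and 0.48/1.47 = 0.33 standard errors.

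**7. If the tool does stratify by site but the model omits it.** The model's SE is too large by a factor 1/sqrt(1 − R-squared). True alpha = 2 × [1 − Φ(1.96/sqrt(1 − R-squared))], which is 0.049, 0.048 or 0.044 for R-squared of 0.01, 0.02 or 0.05.

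**8. Looking at arms by site.** For the powered contrast, each site has 50 vs 100.
- SE of the between-site difference in effect = 12 × sqrt(2 × (1/50 + 1/100)) = 2.94, twice the main SE.
- Power for a 5-point interaction is about 40%.
- With three arms and two sites the full interaction takes (3 − 1) × (2 − 1) = 2 df.

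**The case against.** The documents are silent on the web tool's settings, so stratification by site is neither stated nor ruled out. The mixed model's random effects are also unspecified, so site might enter there. Both points stand, which is why the finding is that site is not in the *described* allocation or the *listed* covariates. Step 7 shows that a site term is still worthwhile if the tool stratifies.

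The plan has features that make large site effects less likely: one manual, training that involves its author, independent review of a sample of recorded sessions, telephone delivery, and outcomes that participants enter themselves into one database. This also stands. The site differences used above are assumptions, and the true one may be smaller.

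A reader might infer more than the documents support:

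- *That site and arm are confounded.* They are not. Participants are individually randomised among all three arms, so only chance imbalance is in question. Without stratification, the unadjusted test's usual standard error already allows for that imbalance on average over repeated trials.
- *That site is the only marker of who delivered CBT.* Section 5.3 lists three primary interventionists at Washington, and its fidelity procedures correct individual therapists, so sessions must be traceable to a therapist. Site is a coarse proxy.
- *That a site term deals with therapist differences.* Therapists act only in the two arms containing CBT. A site main effect removes the average site difference and leaves those effects in place. Capturing them needs an arm-by-site or therapist term, which is not free.

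**Conclusion.** The point holds as a minor, low-cost improvement. Site is missing from the described randomisation and from the listed covariates of a two-site trial, so chance site imbalance and between-site variance go uncorrected. The likely distortion of the primary contrast is under half an MFIS point at the 95th percentile of imbalance. That rests on unstratified allocation, 150 completers per site and a site difference of 2 to 4 points, all assumed. If allocation is stratified, the consequence is slight conservatism. Neither case undermines the primary comparison or the sample size. The reason to act is that the remedy costs at most about 0.3 percentage points of power in the scenarios examined (0.924 to 0.921) and settles the question before the data are seen.

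**What to change.** - **Section 9.2:** add site as a fixed effect to the Aim 1 model and to the models patterned on it. Say whether baseline MFIS is part of the response vector. If it is, include site-by-visit as well, because a constant site effect shifts every visit equally and cancels out of the change from baseline.
- **Section 6.3:** state whether the tool stratifies by site.
- **Reporting:** show arm effects by site with confidence intervals, labelled descriptive. Do not treat a non-significant arm-by-site test as evidence of consistent CBT delivery.

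**Cost:** wording, plus one df for site. With site-by-visit over all four visits (baseline, 8, 12 and 24 weeks) the site terms take 1 + 3 = 4 df. Power stays at about 92%. No added participants, visits or data are needed.

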6.4 Interventions: see also section 5.3

Participants assigned to modafinil or combination therapy will be encouraged to pick up their first supply of modafinil within 7 days of the baseline visit. For virtual visits, participants will receive their first supply of modafinil by mail.

For those who receive CBT or combination therapy will also be able to schedule their first CBT session with the study team during or shortly after this baseline visit.

Participants will be instructed to start their assigned treatment following the 7-day home monitoring period. All treatments will be given for a total of 12 weeks, and treatments will begin after participants complete their first 7-days of PRO-Diary home monitoring.

6.5 Week 8, Week 12, and Week 24 Visits

Group 1 (CBT monotherapy): Participants will have the option of completing all post-baseline REDCap assessments (week 8, 12, and 24) remotely (computer based assessments via weblink which will be provided, or paper forms by mail) or in-person. An internet-connected device will be provided by the study staff member for the participant to complete the REDCap assessments if they choose to complete them during the study visit.

For Week 12 home monitoring period, the watch and instructions for completing the monitoring and for returning the monitor following the 7-day monitoring period (accompanied by a pre-paid return envelope) will be mailed to participants, so that the materials are delivered to the participant ahead of the start of the 11th week. The study staff member will place a reminder call to the participant on or around the first day of the Week 12 home monitoring period and will answer any questions that participant has about completing the Week 12 home monitoring.

Group 2 (Modafinil monotherapy)*: Participants will have the option of completing all REDCap assessments remotely (computer based assessments via weblink which will be provided, or paper forms by mail), or in-person. An internet-connected device will be provided by the study staff member for the participant to complete the REDCap assessments if they choose to complete them during the study visit. Participants will be able to receive drug refill at 8-week either in-person at UMHS (for in-person visit) or in the mail (for virtual visit). Participants will be encouraged to complete the Week 12 REDCap assessment during the final (12th) week of treatment, as close to the end of treatment as possible. For Week 12 home monitoring period, the PROdiary and instructions for completing the monitoring and for returning the PROdiary following the 7-day monitoring period (accompanied by a pre-paid return envelope) will be mailed to participants, so that the materials are delivered to the participant ahead of the start of the 11th week. The study staff member will place a reminder call to the participant on or around the first day of the Week 12 home monitoring period and will answer any questions that participant has about completing the Week 12 home monitoring. Participants will be asked to report number of remaining modafinil pills at the end of the treatment period and can either bring back any unused modafinil to the study personnel to properly dispose of it, or receive the drug destroyer via mail at the end of the 12-week treatment interval to properly dispose of any unused modafinil.

Group 3 (Combination therapy)*:

Participants will have the option of completing all REDCap assessments remotely (computer based assessments via weblink which will be provided, or paper forms by mail), or in-person. An internet-connected device will be provided by the study staff member for the participant to complete the REDCap assessments if they choose to complete them during the study visit. Participants will be able to receive drug refill at 8-week either in-person at UMHS (for in-person visit) or in the mail (for virtual visit).

Participants will be encouraged to complete the Week 12 REDCap assessment during the final (12th) week of treatment, as close to the end of treatment as possible. For Week 12 home monitoring period, the PROdiary and instructions for completing the monitoring and for returning the PROdiary following the 7-day monitoring period (accompanied by a pre-paid return envelope) will be mailed to participants, so that the materials are delivered to the participant ahead of the start of the 11th week. The study staff member will place a reminder call to the participant on or around the first day of the Week 12 home monitoring period and will answer any questions that participant has about completing the Week 12 home monitoring. Participants will be asked to report number of remaining modafinil pills at the end of the treatment period and can either bring back any unused modafinil to the study personnel to properly dispose of it, or receive the drug destroyer via mail at the end of the 12-week treatment interval to properly dispose of any unused modafinil.

Participants who might be at risk for a sleep disorder (obstructive sleep apnea, restless leg syndrome, excessive daytime sleepiness, and clinical insomnia) which might require further evaluation or treatment based on assessments administered during the study will be notified by letter after their 12-week visit. The letter will recommend that they share the information with their primary care doctor.

6.6 Assessment Windows

Day 1 (start of Week 1) is designated as the point at which treatment starts; this will be somewhere between 7 and 14 days after the baseline visit where randomization occurred. The treatment window is the 12 weeks between Day 1 and the end of Week 12.

Efforts will be made to ensure that assessments are gathered as close to the target assessment time points (Week 8, Week 12, and Week 24) as possible; however, unexpected circumstances often arise that make data collection at very specific time points difficult. Therefore, we have established the following assessment windows. If a participant is not able to complete the assessment during the designated assessment window, they will be allowed to stay in the study (at the site investigator discretion), completing any later assessments as they are able and willing.

Protocol deviations will be completed for participants completing the assessments out of window, with the exception of the prescreening to screening assessment window. Protocol deviations will not be reported for self-report survey data. Self-reported survey data at the baseline, 8 week, 12 week and 24 week surveys is not being collected to assess safety-related information (e.g., side effects, AEs). As is standard, participants are not required to answer any self-reported survey questions they do not wish to answer, and some participants opt to skip questions/surveys they are not comfortable with. If participants skip a question(s) on the surveys (administered online via REDCap), they will be prompted by REDCap that they have missed a question(s) and they can go back and answer or choose to proceed without answering. We have found that in previous studies, skipping questions is rare, and thus we do not expect it to affect data validity.

Additionally, protocol deviations will not be reported for missed EMA assessments administered by the PRO-Diary data during the home monitoring periods. We expect that there may be instances where participants are unable to complete the EMA questions (for example, if it alerts at a time that is inconvenient for them to answer or they forget to answer). Previous studies have shown that compliance with these repeated assessments is ~75%. The EMA assessments do not assess safety so a missed assessment is not a safety concern. We expect that participants will miss some of these assessments and have selected the length of the home monitoring periods (7 days) to make sure data validity is not compromised if participants miss some of the EMA assessments.

Any missed safety assessments will be reported as protocol deviations. Safety assessments are conducted by the coordinator in-person or by phone as applicable under the supervision of the study PIs during the baseline, 8 week, 12 week and 24 week study visits and during any other contact with the participant (e.g., phone calls).

1. Prescreening to Screening/Baseline Assessment Window: Study staff will aim to schedule the screening/baseline visit within 2 weeks of pre-screening. If the baseline visit is beyond 2 weeks from pre-screening, a study staff member will ask prior to the visit if there has been any change (in fatigue, meds, pregnancy, MS relapses, etc.) since pre-screening.
2. Baseline Home Monitoring Assessment Window: Participants will be given 14 days from their Baseline visit to complete their 7-day home monitoring period assessment. Although participants are asked to complete 7 days of home monitoring, a minimum of 3 full days of home monitoring data will be considered adequate (this allows for lost data due to technology malfunction/user error/illness/etc.).
3. Week 8 Assessment Window: A \pm 2-week (\pm 14 days) window around the Week 8 assessment will be considered allowable for data collection, as long as participants have not allowed modafinil treatment to lapse/run out during this time period.
4. Home Monitoring Prior to Week 12: The Week 12 PRO-Diary home monitoring data collection will ideally commence 7 days prior to the final day of modafinil administration. A minimum of 3 days of monitoring during the final week of modafinil administration will be acceptable for completion of this data collection, as no monitoring should take place after modafinil has stopped; monitoring will cease following the last day of modafinil treatment even if an entire 7 days of data has not been collected.
5. Week 12 Assessment Window: The Week 12 survey (REDCap) assessment can be completed up to 2 weeks (-14 days) prior to the Week 12 visit, but if possible should be completed within the final week of modafinil treatment, and no later than final day of modafinil administration.

6. Week 24 Assessment Window: A \pm 1-month (\pm 30 days) window around the Week 24 period will be allowed for collection of follow-up data.

